137 with this chronic medical condition ^{17,18}. In the T1DX registry an average HbA1c of 8.2%, which
138 is well above the recommended target of <7.5% for children, has been noted ¹⁷. Indeed, only
139 21% of T1D adolescents (ages 13-20) had HbA1c levels <7.5%; and less than half of those 6-12
140 years of age achieved an HbA1c <8% ¹⁹. This increased HbA1c reflects chronic abnormal
141 glucose metabolism, and is associated with diabetes complications and reduced lifespan ²⁰.

142
143 **Newly available hybrid closed loop (HCL) therapy offers the potential for true chronic**
144 **near-normalization of metabolic control.**

145 A major problem for previous studies trying to assess the impact of interventions in the first year
146 of T1D diagnosis has been that the vast majority of the new-onset population is in a honeymoon
147 phase, and this combined with improvements in diabetes care have made it difficult to observe
148 differences in metabolic control between the intervention and usual care cohorts ¹⁶. However, our
149 tools have recently been refined with the approval of the first HCL system, the MiniMed 670G,

150 garnering FDA approval in September 2016. Recently, the labeling has been expanded to include
151 children down to age 7 years. A study including fifty 2-6 year old patients was completed and
152 submitted to the FDA in 2019. HCL insulin delivery is a major leap forward, as it provides more
153 physiologic insulin delivery since basal insulin delivery is based on sensor glucose values.
154 Highlighting the safety of HCL, in the pivotal trial in 124 participants (including 30 adolescents)
155 that allowed for regulatory approval of the system, there were no episodes of either severe
156 hypoglycemia or DKA ¹⁴. Importantly, over a 3-month period, HbA1c levels and the proportion
157 of time in-target range based on sensor glucose values improved. In addition to improving
158 glucose time-in-range, decreased glycemic variability was seen in participants when using HCL
159 therapy compared to a 2-week baseline data collection phase where they were using sensor-
160 augmented pump therapy without automation of insulin delivery ²¹. Decreased glycemic
161 variability is associated with C-peptide preservation at 1 and 2 years post diagnosis ^{15,22},
162 suggesting that technologies that can further normalize glycemic variability may have an even
163 greater impact. Early real-world findings evaluating MiniMed 670G data obtained in the 6-

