2. EKG
For Cohort A, an EKG will be performed at Screening and at the 6, 26, and 52 week visits. The screening EKG must be read by a pediatric cardiologist to ensure there is no underlying abnormality that precludes study participation. The automated reading will be acceptable if normal for subsequent EKGs. Any automated EKG readings suggesting abnormalities in QTc and/or PR intervals will be referred to a pediatric cardiologist for interpretation.
3. Liver function tests
For Cohort A, AST/ALT will be measured locally at Screening and at the 6, 26, and 52 week visits
4. Kidney tests
For Cohort A, creatinine will be measured locally at Screening and used to calculate eGFR
5. Urine or serum pregnancy:
Performed locally for females with childbearing potential at Screening and each follow up visit, and also anytime pregnancy is suspected. Must be negative to perform the MMTT.
6. MMTT:
2-hour MMTT for stimulated glucose and C-peptide will be done at Randomization, 13, 26, 39, and 52 week visits, with samples collected at 0, 15, 30, 60, 90 and 120 minutes. Criteria will be detailed in the site procedures manual.

903 7. HbA1c:
904 Collected for central lab analysis at Randomization, 13, 26, 39, and 52 week visits
905 8. Measures of beta cell health and immune function:
906 Blood/serum/plasma will be drawn and sent to the appropriate lab, to assess several
907 measures detailed below. Samples at some of the time points may or may not be run
908 depending on final study results.

909 i. Pro-insulin and Pro-IAPP and their ratios to C-peptide during the MMTT at 0 and
910 90 minutes, collected at Randomization, 13, 26, 39, and 52 week visits
911 ii. Circulating unmethylated INS DNA, collected at Randomization, 13, 26, 39, and
912 52 week visits
913 iii. Circulating plasma miRNA sequencing, collected at Randomization, 13, 26, 39,
914 and 52 week visits
915 iv. T-cell characteristics by PBMC and peripheral cytokine levels, collected at
916 Randomization, 26 and 52 week visits only.
917 v. Collection and storage of extra samples of plasma as blood volume limitations for
918 size allow and/or storage of any remaining samples for future research, collected at
919 Randomization, 26, and 52 week visits only, as approved by the participants.

920
921 *Local laboratory testing will be performed if needed to screen for exclusionary medical*
922 *conditions.*

Chapter 8: Unanticipated Problems, Adverse Events, Device Issues, and Stopping Rules

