183 minutes, 30 minutes, 60 minutes, 90 minutes, and 120 minutes.
184 • At least one C-peptide measurement available at 90 minutes or 120 minutes.
185 • No two consecutive C-peptide measurements missing.

186
187 If any of these conditions is violated, the C-peptide AUC will be treated as a missing value for
188 that visit. If it is discovered that the MMTT was completed while the participant was in closed
189 loop or while the participant was not fasting, those MMTT results will also be treated as missing
190 for that visit.

191
192 If the lab deems the C-peptide AUC value to be below the lower limit of detection (LLOD), the
193 C-peptide value will be assigned the value of $\frac{1}{2}$ of the LLOD, akin to TrialNet (3).

194
195 For each MMTT, the starting time of the MMTT will be defined as t=0 if the C-peptide value is
196 available at that time point.

197
198 The trapezoidal rule will be used to calculate the stimulated C-peptide AUC as a weighted sum
199 of the C-peptide measurements. Throughout the calculation, target times for C-peptide
200 measurements will be used (as opposed to the actual measurement times).

201
202 If the C-peptide measurement at 120 minutes is not available, the following steps will be used to
203 calculate AUC:

204 • Calculate AUC₉₀ from C-peptide measurements taken between baseline and 90 minutes
205 • Calculate AUC as AUC₉₀ \times (120/90)

206
207 *Peak*

208 This will be defined as the maximum of all C-peptide values during the MMTT, which can occur
209 at t=0. The rules for handling any missing measurements during the MMTT will be the same as
210 listed above for the AUC. Thus, peak C-peptide will be missing for a visit if and only if C-
211 peptide AUC is also missing.

212 **5.2 CGM Metrics**

213 Note that no pre-randomization CGM data are collected in this protocol (new onset patients) so no
214 baseline CGM metrics will be calculated.

215
216 Participants assigned to a non-HCL group will be provided a commercially available Dexcom G6
217 CGM. Participants who stop using a CGM or have insufficient CGM data will wear a blinded
218 Dexcom G6 for approximately 10 days at 6, 13, 26, 39 and 52 weeks. The CGM indices listed
219 above will be computed separately at each follow-up visit including all unblinded data 28 days
220 prior to the visit date and any data from a blinded sensor placed at the visit (or prior to the visit at

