295 analysis is \geq 95% of the N in the primary intent-to-treat analysis.

296

297 **8. Secondary Analyses**

298 As described above for the primary analysis, comparisons of HCL versus non-HCL will include
299 cohorts A and B and will be pooled over verapamil groups. Comparisons of verapamil versus
300 placebo will be limited to Cohort A and will be pooled over HCL and usual care groups.

301

302 Descriptive summary statistics appropriate to the distribution will be given for each secondary
303 efficacy outcome listed above in Section 5 by treatment group at each visit. Corresponding
304 boxplot figures of baseline and 52 weeks, boxplot figures over time, scatterplots of baseline
305 versus 52 weeks, and histograms of baseline, 26 weeks, and 52 weeks will be constructed for
306 selected metrics.

307

308 **8.1 Formal Statistical Comparisons of Treatment Groups**

309

310 C-peptide Related Secondary Efficacy Outcome

311 Formal statistical comparisons of treatment groups will limited to C-peptide AUC at 13, 26, and
312 39 weeks (52 weeks is the primary analysis described above).

313

314 Other Secondary Efficacy Outcomes

315 Formal statistical comparisons of treatment groups for other secondary efficacy outcomes will be
316 limited to the following at 26 and 52 weeks:

317 • Mean HbA1c
318 • Total daily insulin per kg
319 • Selected overall (24 hours) CGM indices:

320 ➤ Mean glucose
321 ➤ Percentage of time sensor glucose from 70 to 140 mg/dL
322 ➤ Percentage of time sensor glucose from 70 to 180 mg/dL
323 ➤ Percentage of time sensor glucose >180 mg/dL
324 ➤ Percentage of time sensor glucose >250 mg/dL
325 ➤ Percentage of time sensor glucose <54 mg/dL
326 ➤ Percentage of time sensor glucose <70 mg/dL

327

328 Separate comparisons for HCL versus non-HCL and verapamil versus placebo will be done
329 similarly as described above for the primary analysis. Except where noted otherwise below in
330 Sections 8.3 and 8.5, the general approach for analysis of secondary outcomes will be as follows:
331 For each outcome, a constrained longitudinal model will be fit adjusting for age, time from
332 diagnosis to randomization, verapamil group (for HCL analysis), HCL group (for verapamil

333 analysis) and clinical site as a random effect. A treatment by time interaction will be included in
334 the model and treatment effects (and 95% CI) will be reported separately at 26 and 52 weeks.

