374 listed above and will be limited to the 24 hour versions (analysis of daytime and nighttime versions
375 will be descriptive only). Analysis will follow the method described above with three exceptions:

- 376 • The longitudinal model will not be constrained because no baseline values will be
377 available.
- 378 • The unconstrained longitudinal model will include 6 week values.
- 379 • For verapamil vs. placebo comparisons the type of CGM sensor used (Medtronic, Dexcom)
380 will be included as a covariate in the models. This covariate will be allowed to differ within
381 subject if the participant changes devices between visits. If the participant switches sensors
382 in the 28 day period used to calculate CGM metrics, data from both sensors will be used to
383 calculate metrics and the value for the sensor covariate will be set equal to the sensor which
384 contributed the most data.

385
386 It is likely that percentage of sensor values below 54 mg/dL and possible that the percentage of
387 sensor values above 250 mg/dL will have a skewed distribution. The other CGM metrics are
388 anticipated to have an approximate normal distribution. As described above for the primary
389 analysis, robust regression with M-estimation will be used to analyze skewed outcomes.

390
391 The percentage of patients with $\geq 70\%$ of sensor values from 70 to 140 mg/dL will be analyzed
392 using generalized estimating equations (GEE) logistic regressions adjusting for baseline HbA1c,
393 age, time from diagnosis to randomization. Clinical site will be treated as a repeated factor using
394 a compound symmetry covariance structure. A risk-adjusted difference and 95% confidence
395 interval for the percentages will be calculated using the method of Kleinman and Norton (4). This
396 analysis will be available cases only. There will be no imputation of missing data.

397 398 9. Interaction Analyses

399 A factorial design is being used for this study because it is believed to be unlikely that the device
400 (HCL) and drug (verapamil) would interact with each other. An interaction test will be
401 conducted to explore this assumption. This analysis will be limited to cohort A. Note that this
402 study has not been powered to detect interaction. Thus, this analysis is considered exploratory
403 and no primary conclusions about the efficacy of either HCL or verapamil will be based solely

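### The continuous CGM models in SAP 8.5 leave out HbA1c and C-peptide AUC at randomization, which may cost precision on secondary objective 1

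*SAP*

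**What the plan says.** SAP 8.1 sets the general method for secondary outcomes: "For each outcome, a constrained longitudinal model will be fit adjusting for age, time from" "diagnosis to randomization, verapamil group (for HCL analysis), HCL group (for verapamil" analysis), with clinical site as a random effect.

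SAP 5.2 explains why CGM differs: "Note that no pre-randomization CGM data are collected in this protocol (new onset patients) so no" baseline CGM metric can be computed. SAP 8.5 therefore applies the general method to the continuous CGM indices with three exceptions:

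- The model is unconstrained: "The longitudinal model will not be constrained because no baseline values will be" available.
- The 6-week values are included.
- Sensor type is a covariate, for verapamil versus placebo only.

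None of the three brings in HbA1c or C-peptide at randomization. Both exist. Protocol 7.2 says "2-hour MMTT for stimulated glucose and C-peptide will be done at Randomization, 13, 26" and later visits, and the same section lists a central-laboratory HbA1c at randomization.

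Later in SAP 8.5, the responder outcome (share of participants with at least 70% of readings in a target range) is to be analysed "using generalized estimating equations (GEE) logistic regressions adjusting for baseline HbA1c", age and time from diagnosis. No reason is given for using baseline HbA1c there and not in the continuous models.

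**The concern.** SAP 6.1 notes that the constrained model is equivalent to adjusting for the baseline value of the outcome. C-peptide, HbA1c and daily insulin dose all have a randomization value and so get that adjustment. Among the efficacy outcomes that are formally compared, only the CGM indices lose it, and no proxy is substituted.

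The sponsor's own text suggests that a proxy could help. Protocol 1.1 says that most newly diagnosed patients are in a honeymoon "phase, and this combined with improvements in diabetes care have made it difficult to observe" differences in control between groups. C-peptide at randomization is the trial's direct measure of residual function. SAP 12.5 also plans to model C-peptide against time in range.

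The precision of these comparisons matters for more than secondary objective 1. Protocol 10.4 also uses the CGM metrics to judge whether the HCL arm reached near-normal glycemia and separated from control, which the primary HCL hypothesis requires. If baseline variation that could be explained stays in the residual, those intervals are wider than they need be.

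No other provision covers this. Protocol 2.4 stratifies by site only and leaves imbalance in key variables to the analysis, but SAP 10.1 adds imbalanced covariates to the primary analyses only.

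**Working it through.** **The plan's own figures.** The documents give power only for C-peptide AUC; there is no SD, power or target precision for any CGM metric. The stated figures reproduce:

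- Verapamil: difference 0.126, SD 0.18, two-sided 5%, 90% power. n per arm = 2 × (1.960 + 1.282)² × 0.18² / 0.126² = 42.9, so 43 per arm, or 86. By the noncentral t, 44 per arm gives 90.1%, which matches the stated 88. Dropout: 88/0.90 = 97.8, so 98.
- HCL: 71 × 0.9 ≈ 64 and 60 × 0.9 = 54. Power is 96.6% (normal) or 96.4% (t), against the stated 96%.

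These figures are unaffected by the present point. They supply the sample sizes used below: 64 + 54 = 118 and 88.

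**Effect of adding two baseline covariates.** Inputs:

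- N = 118 (HCL) and 88 (verapamil), from SAP 4.
- Four fixed covariates besides treatment. HCL: age, time from diagnosis and two indicators for drug group. Verapamil: age, time from diagnosis, HCL and sensor type.
- Residual degrees of freedom before the change: df0 = N − 2 − 4, that is 112 and 82.
- Assumption, not in the documents: R² is the share of the remaining variance in a CGM metric that randomization C-peptide and HbA1c explain together. The range shown starts at zero.

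Single-visit approximation: variance ratio = (1 − R²) × (df0 − 1)/(df0 − 3). The second factor is the price of two extra coefficients: 111/109 = 1.018 (HCL) and 81/79 = 1.025 (verapamil). The change in interval width is the square root of the ratio, minus 1.

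| Assumed added R² | CI width, HCL (N = 118) | CI width, verapamil (N = 88) | HCL contrast planned at 80% power becomes |
|---|---|---|---|
| 0 | +0.9% | +1.3% | 79% |
| 0.04 | −1.1% | −0.8% | 81% |
| 0.09 | −3.7% | −3.4% | 83% |
| 0.16 | −7.5% | −7.2% | 86% |
| 0.25 | −12.6% | −12.3% | 89% |

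Worked line, HCL at R² = 0.16: 0.84 × 1.018 = 0.855; √0.855 = 0.925; width −7.5%.

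Break-even R²: 1 − 109/111 = 0.018 (HCL) and 1 − 79/81 = 0.025 (verapamil).

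**Chance imbalance is not a second gain.** Take a correlation of r = 0.4 (R² = 0.16). The part of the standard error of the HCL contrast that comes from chance imbalance in the covariate is r × √(1/64 + 1/54) = 0.4 × 0.185 = 0.074 SD of the metric. Its square is r² times the unadjusted variance, which is exactly what the factor (1 − R²) removes. It must not be counted again.

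**Limit of the formula.** It describes least-squares or likelihood estimation at one visit. It does not carry over directly to metrics analysed by M-estimation, such as time below 54 mg/dL and possibly time above 250 mg/dL.

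**The case against.** The strongest case against acting is that the gain is unknown and may be nil. The documents quantify no link between baseline C-peptide or HbA1c and later CGM values. The honeymoon sentence in Protocol 1.1 is about blurring of the contrast between groups, together with better care; it does not say that baseline C-peptide explains differences between children at 26 and 52 weeks, when the formal tests are made. Baseline is within 31 days of diagnosis, so it can precede the last test by most of a year. A closed-loop algorithm aiming at near-normal glucose could weaken the correlation in its arm. All of this stands, and it is why the table starts at zero.

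Three stronger readings are tempting, and the documents do not support them:

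- A reader might infer that these models have no baseline adjustment at all. They do: age and time from diagnosis remain, and Protocol 1.1 calls age the strongest predictor of C-peptide decline. Part of the relevant variation may already be modelled.
- A reader might infer that chance imbalance in residual function biases the CGM comparison. Randomization keeps the comparison valid, and its interval already allows for chance imbalance.
- A reader might infer that the change is strictly free. It costs about 1% in interval width if the covariates are uninformative.

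The responder model is also a weak template. SAP 8.5 describes its range as 70–140 mg/dL where SAP 2 and SAP 5 use 70–180; SAP 8.1 omits it from the formal comparisons; and it leaves out the other randomized factor. The inconsistency over baseline HbA1c therefore calls for an explanation but does not show which model is right.

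Other analyses give partial cover. Mean HbA1c at 26 and 52 weeks is compared in a constrained model that uses its own baseline. SAP 11 examines time in range by randomization HbA1c and C-peptide, but only as exploratory interaction tests and only after a significant primary result.

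**Conclusion.** The point holds as a low-cost efficiency improvement to secondary analyses. The continuous CGM models omit two baseline measures that are already collected and plausibly prognostic, and the SAP gives no reason. Validity is not in question and no primary figure changes.

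The size depends wholly on an assumed added R². Over the range 0 to 0.25, interval width moves from about 1% wider to about 13% narrower for HCL versus non-HCL, and from 1.3% wider to 12.3% narrower for verapamil versus placebo. An added R² of only about 0.02 pays for the two covariates. The possible loss is therefore small and bounded, and the possible gain is larger. The documents support the prognostic role of residual C-peptide only qualitatively, so no particular gain can be promised.

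**What to change.** Amend SAP 8.5 to state that every continuous CGM longitudinal model, for both comparisons, includes log(C-peptide AUC+1) and HbA1c at randomization as fixed covariates, each with a by-visit term. Because the unconstrained model loses the constrained model's handling of missing baselines, add a rule: replace a missing baseline covariate by its overall mean, computed without regard to arm, so that no participant is dropped. Add baseline C-peptide to the responder model, which already has HbA1c. If the sponsor prefers to keep the continuous models as they are, the SAP should say why only the responder model uses baseline HbA1c.

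The change should be fixed before any unblinded CGM comparison. SAP version 2.0 added sensor type to the verapamil CGM models while follow-up was ongoing, so an amendment of this kind has precedent.

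The cost is a short addition to the SAP and no new data. With by-visit terms over five visits (6 to 52 weeks) each model gains ten coefficients, about two per visit contrast. The statistical price is about 1% in interval width if the covariates turn out to be uninformative.

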1415 The Statistical Analysis Plan (SAP) will describe how CGM derived indices will be calculated.

1416 1417 HbA1c

1418 HbA1c levels will be used as a measure of hyperglycemia.

1419

1420 HbA1c outcomes at 13, 26, 39, and 52 weeks will include the following:

- Mean HbA1c
- Percentage of patients with an HbA1c <7.0% and <6.5%

1423

1424 **10.5 Analysis Datasets**

1425 The primary analysis will follow the intention-to-treat principle. It will include all randomized
1426 participants, and data will be analyzed based on the treatment assigned from randomization
1427 regardless of the actual treatment received.

1428

1429 A per-protocol analysis that includes participants adhering to the protocol will be performed and
1430 detailed in the SAP. Sensitivity analyses on the primary outcome will be described in the SAP.

1431

1432 All participants will be included in safety analyses.

1433 **10.6 Analysis of the Primary Efficacy Endpoint**

1434 Both primary analyses will follow the intention-to-treat principle.

1435 **10.6.1 HCL vs. non-HCL Analysis**

1436 The HCL/intensive care versus non-HCL/standard care comparison will combine participants
1437 from Cohort A and B. A constrained longitudinal analysis will be performed by fitting the
1438 baseline (randomization) and 52 week log(AUC+1) as the outcome and testing for device use
1439 indicator (randomized to HCL/intensive therapy or randomized to no HCL/standard therapy)
1440 controlling for age, time from diagnosis to randomization, and drug use indicator (verapamil,
1441 placebo, or no drug [Cohort B]). The log(AUC+1) transform is expected to make the residuals
1442 approximately normally distributed, but regression diagnostics will be performed to check the
1443 residuals and an appropriate alternative transformation or a nonparametric analysis based on
1444 ranks will be performed if the residuals have a skewed distribution. The primary analysis test
1445 assumes there is no interaction between device use and drug use; an analysis described below
1446 will assess possible treatment interactions.

1447 **10.6.2 Verapamil vs. Placebo Analysis**

1448 The verapamil vs. placebo comparison will only include participants in Cohort A. A similar
1449 constrained longitudinal analysis will be performed except testing for the drug use indicator
1450 (randomized to verapamil or randomized to placebo) and controlling for device use (HCL or no
1451 HCL).

1452 **10.7 Analysis of the Secondary Endpoint**

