104 MMTT at 52 weeks between HCL with intensive care and non-HCL with standard care
105 for the combined Cohort A and B population.
106 • *Alternative Hypothesis:* There is a nonzero difference in the C-peptide AUC in response
107 to a 2-hour MMTT at 52 weeks between HCL with intensive care and non-HCL with
108 standard care for the combined Cohort A and Cohort B population.

109
110 **3.2 Verapamil vs. Placebo**

111 • *Null Hypothesis:* There is no difference in the C-peptide AUC in response to a 2-hour
112 MMTT at 52 weeks between verapamil and placebo for the Cohort A population.
113 • *Alternative Hypothesis:* There is a nonzero difference in the C-peptide AUC in response
114 to a 2-hour MMTT at 52 weeks between verapamil and placebo for the Cohort A
115 population.

116
117 **4. Sample size**

118 The sample size calculation is detailed in a separate document and is summarized below. Sample
119 size was driven by the verapamil vs. placebo comparison as the test only includes participants in
120 Cohort A. The mean of the transformed C-peptide ($\log(AUC + 1)$) and the root mean square
121 error in the placebo group were assumed to be 0.315 and 0.18, respectively, based on 90% CIs
122 from prior studies (1). The corresponding geometric-like mean C-peptide value of 0.370
123 pmol/mL was calculated using the inverse transformation: $\exp(0.315) - 1$. A recent randomized
124 trial (2) found a 62% increase in mean C-peptide in verapamil compared with placebo, although

125 the total sample size was small (N=24) and confidence intervals were wide. Therefore, this
126 study assumed a smaller, 50% increase in mean C-peptide using verapamil. The expected
127 geometric-like mean C-peptide value in the verapamil arm was $0.370 \cdot 1.50 = 0.555$ pmol/mL.
128 After a $\log(x+1)$ transformation, the mean values in the control and treatment groups are 0.315
129 and 0.441, respectively, giving a treatment effect of $0.441 - 0.315 = 0.126$.

130 With these estimates, a sample size of 88 participants in Cohort A was calculated to provide 90%
131 power with a 5% two-sided type 1 error rate and a 1:1 treatment group allocation to detect a
132 verapamil vs. placebo treatment group difference assuming the true relative difference between
133 groups was 50%. To account for a 10% dropout rate, the sample size in Cohort A will be 98
134 participants.

135 A sample size of 33 participants for Cohort B was selected based on convenience. Participants

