404 on the results of this analysis. If the interaction term is significant, separate results also will be
405 reported (described below).

406 In cohort A, the same constrained longitudinal analysis model described above for the primary
407 analysis of C-peptide AUC at 52 weeks (Section 7.2) will be fit with the addition of a device by
408 drug interaction. If there is evidence for an interaction at 52 weeks ($p < 0.05$), the following
409 additional analyses will be performed:

- 410 • Baseline Characteristics

411 A separate table for Cohort A, one column for each of the 4 combinations of HCL and
412 Verapamil.

- 413 • HCL vs. non-HCL

Summary statistics for C-peptide AUC at 52 weeks will be given separately for each of the 4 treatment group combinations. Boxplots will be given for baseline, 6, 13, 26, 39 and 52 weeks with one box for each of the 4 treatment combinations at each visit. The point estimate, 95% confidence interval and p-value at 52 weeks will be given from the model described above for the HCL effect separately in the verapamil and placebo groups. The HCL effect will also be estimated separately in cohort B.

- Verapamil vs. Placebo

Analogous analyses will be performed as described in the previous bullet reversing the roles of HCL and verapamil (Cohort A only).

10. Sensitivity Analyses

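### SAP 9 shows results for the four factorial cells only if an interaction test it calls unpowered gives p<0.05; for interactions below about 0.15 on the log(AUC+1) scale, the cell results would more often than not go unreported.

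*SAP*

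**What the plan says.** Protocol 10.6.1 states that the primary test "assumes there is no interaction between device use and drug use; an analysis described below" is meant to examine that assumption. SAP 6.1 pools the HCL comparison over verapamil groups, and SAP 6.2 pools the verapamil comparison over device groups.

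SAP 9 considers an interaction unlikely, restricts the test to Cohort A, and is open about its limits: the "study has not been powered to detect interaction. Thus, this analysis is considered exploratory". It bars primary conclusions that rest solely on this test. It then adds a device-by-drug term to the primary model and sets the trigger: "drug interaction. If there is evidence for an interaction at 52 weeks", defined as p<0.05. Only then are the following produced:

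- the four-column baseline table ("A separate table for Cohort A, one column for each of the 4 combinations of HCL and" verapamil);
- 52-week C-peptide AUC summaries, and boxplots by visit, for the four combinations;
- the effect of each intervention within levels of the other.

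SAP 12.5 puts the same condition on the four-combination curves relating C-peptide to glycemic control. SAP 15 otherwise provides two pooled baseline tables. Nowhere does either document commit to reporting the interaction estimate with its confidence interval.

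**The concern.** Cohort A is randomized to four groups, and each pooled effect is a simple summary only if the two interventions act roughly additively. The descriptive evidence on additivity appears only when a weak test happens to be significant. Two things follow.

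First, a moderate departure from additivity would usually leave the reader with pooled results only. Suppose verapamil had its full planned effect without HCL and none with it. The pooled effect would be half the planned one, and the cell means that explain why would probably not be tabulated.

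Second, the condition selects what is shown. Cell results appear only when the estimated interaction exceeds about 0.150 in absolute value. If the true value were 0.126, every triggered estimate in that direction would be at least 19% too large (0.150/0.126 = 1.19).

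**Working it through.** **Inputs (SAP 4, repeated in Protocol 10.3).** Effect 0.126 on log(AUC+1), from 0.441 − 0.315. Placebo mean and root mean square error: "error in the placebo group were assumed to be 0.315 and 0.18, respectively, based on 90% CIs". Two-sided alpha 0.05. There are 88 completers in Cohort A, allocated 1:1:1:1, so 44 per arm and 22 per cell. Protocol 2.1 aims for 30 completers in Cohort B, allocated 2:1, so 20 and 10.

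**Reproducing the plan.** The normal formula gives 43 per arm (86). The t-based version gives 44 per arm (88) with 90.1% power. Then 88/0.9 = 97.8, so 98 randomized. For HCL, 71 and 60 less 10% gives about 64 and 54, with power 96.4% (t) against the stated 96%. The inputs are therefore being read as the plan reads them.

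**Interaction at 52 weeks.** This is the verapamil effect with HCL minus the verapamil effect without HCL, a contrast of four cell means.

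- SE = 0.18 × √(4/22) = 0.0768
- 95% CI half-width = 1.96 × 0.0768 = 0.150
- Power = Φ(|interaction|/0.0768 − 1.96)

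The documents give no interaction size, so a range is shown:

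| Assumed interaction | Multiple of 0.126 | Power |
|---|---|---|
| 0.063 | 0.5 | 12.7% |
| 0.126 | 1.0 | 37.5% (t: 36.8%) |
| 0.150 | 1.19 | 50% |
| 0.189 | 1.5 | 69.2% |
| 0.252 | 2.0 | 90.7% |

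The interaction detectable with 80% power is (1.96 + 0.842) × 0.0768 = 0.215, about 1.7 times the design effect. If all 98 randomized participants were evaluable (24.5 per cell), power at 0.126 would be 41.0%.

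**Exposure of each primary test.**

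- *Verapamil.* If the effect is 0.126 in one device group and 0 in the other, the pooled effect is 0.063, with SE = 0.18 × √(2/44) = 0.0384 and power of about 37.5%. The cell results would not be triggered 62.5% of the time (1 − 0.375).
- *HCL.* If the effect is 0.126 in the placebo group and Cohort B, and 0 in the verapamil group, the precision weights n₁n₂/(n₁+n₂) are 11, 11 and 6.67 for placebo, verapamil and Cohort B. The pooled effect is 0.126 × 17.67/28.67 = 0.078, with SE = 0.18/√28.67 = 0.0336 and power Φ(0.078/0.0336 − 1.96), about 64%.

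**The case against.** The best defence is that SAP 9 hides nothing. It says the test lacks power, labels it exploratory, runs it unconditionally, and keeps primary conclusions off it. A reader might infer that a non-significant result will be presented as proof of additivity. The text does not support that and points the other way. Nor does any section forbid cell summaries when p≥0.05; they are simply not planned.

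The 38% is not a fixed property of the test. It belongs to an assumed interaction of 0.126. A full reversal of the verapamil effect, from +0.126 to −0.126, is an interaction of 0.252 and would be detected about 91% of the time. The SD of 0.18 is also described in SAP 4 as an upper confidence limit. If it were 0.15 (an assumption), power at 0.126 would be about 50%. These points stand, and they limit the claim to interactions below about 0.15 at the planning SD.

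Conditioning the simple effects on the interaction test also has a real purpose. Each simple effect has SE = 0.18 × √(2/22) = 0.054 and about 64% power for 0.126. Under perfect additivity, verapamil would therefore be significant in one device group and not the other about 2 × 0.64 × 0.36 = 46% of the time, which invites a false reading of effect modification. Leaving those estimates and p-values conditional is a defensible trade-off. It also matches Protocol 10.14, which makes the separate effects depend on a significant interaction.

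None of this argues against unconditional cell summaries or an interaction estimate with its interval. Neither adds a test. SAP 10.1 itself judges baseline imbalance clinically, not by p-value. Protocol 10.11 promises baseline tables by treatment group without condition, and the Protocol Summary lists four treatment groups for Cohort A.

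**Conclusion.** The concern holds as a reporting gap. Description of the four randomized cells depends on p<0.05 from a test whose 95% interval extends 0.15 either side of the estimate, more than the whole design effect. At 22 completers per cell and SD 0.18, interactions below about 0.15 would more often than not leave the cell results unreported. For an assumed interaction of 0.126 the chance of that is about 62%.

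A reader might go further and conclude that the primary analyses are invalid, or that both are equally exposed. The documents support neither. Pooling is the stated factorial design, with its assumption declared. The HCL test includes Cohort B, about 30 of 118 completers, who receive no drug. Dilution of a pooled effect under interaction comes from the design and not from the reporting rule, so changing the rule would not restore that power.

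**What to change.** In SAP 9, report for Cohort A whatever the interaction p-value:

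1. the four-column baseline table;
2. C-peptide AUC summaries for the four cells at each MMTT visit (randomization, 13, 26, 39 and 52 weeks);
3. the device-by-drug interaction estimate at 52 weeks with its 95% CI.

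Remove the matching condition on the four-combination curves in SAP 12.5. Keep the exploratory label, keep the primary conclusions on the pooled effects, and leave the simple-effect estimates and p-values conditional as now. Align Protocol 10.14, or record the change in SAP 2.

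The cost is about one extra table or figure and a note that the cell results are imprecise. No new data are needed, and alpha, sample size and the power of the pooled tests are unaffected.
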